11.4.2. Safety Data

Safety data will be summarized for the Safety Analysis Population. Pre-second vaccination, Study Groups 1, 2, 3 will be analyzed jointly as one study group as all three groups received the same vaccine at Day 1.

Solicited AEs will be summarized by severity for each day after each study vaccination (Days 1 through 7 days post-vaccination) and as the maximum severity over all days after each vaccination. The maximum severity of local and systemic reactions will be determined for each subject and summarized by study group following each vaccination (as well as post any vaccination) and the resulting number, percentage (observed rate) of subjects and associated exact 95% confidence interval (CI) will be summarized by severity grade (none, mild, moderate, severe) and symptom. Summaries will also be provided for any systemic symptoms, for any local symptoms, and for any systematic or local symptoms.

Vaccine-related unsolicited AEs from the first study vaccination through 28 days post second vaccination will be coded by Medical Dictionary for Regulatory Activities (MedDRA®) for preferred term and system organ class (SOC). These AEs will be summarized as number and percentage of subjects reporting at least one event in each MedDRA® preferred term and SOC, cross tabulated by severity grade (none, mild, moderate, severe). Additionally, the number, percentage (observed rate) and exact two-sided 95% CI for subjects reporting a related unsolicited AE overall, by SOC, and by preferred term will be summarized by study group.

Clinical safety laboratory AEs from the time of first study vaccination through approximately 28 days after the second vaccination will be summarized by severity grade (none, mild, moderate, severe) for each laboratory visit. In addition, the maximum severity over all post-vaccination visits will be summarized by study visit and by severity grade (none, mild, moderate, severe) using percentages and exact two-sided 95% CIs.

The number of SAEs and vaccine-related Medically Attended Adverse Events (MAAEs) through 6 months post first vaccination will be reported by detailed listings showing the event description, preferred term and SOC, relevant dates (study vaccinations and AEs), severity, vaccine-relatedness, and outcome for each event.

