3.2. Study Outcome Measures

3.2.1. Primary

- Frequency and severity of solicited local and systemic reactogenicity from the time of study vaccine administration through 7 days post-vaccination.
- Frequency and severity of vaccine-related unsolicited adverse events (AEs) from the first study vaccination through 28 days post second vaccination.
- Frequency and severity of clinical safety laboratory AEs from the time of first study vaccination through approximately 28 days after the second vaccination.
- Frequency of Serious Adverse Events (SAEs) and vaccine-related Medically Attended Adverse Events (MAAEs) through 6 months post first vaccination.

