6.5. Missing Data

Unless otherwise specified, missing data will be maintained as missing for all analyses and no imputation will be performed for missing values.

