9. SAFETY EVALUATION

All safety analyses will be presented using the safety population. Any medical condition that is present at the time that the subject is screened will be considered baseline and not reported as an AE, unless it worsens in severity or increases in frequency during the study. When calculating the incidence of solicited and unsolicited adverse events (i.e., on a per subject basis), each subject will be counted once and any repetitions of solicited and unsolicited adverse events within a subject will be ignored; the denominator will be the number of subjects in the safety analysis population unless results are shown by dose in which case the denominator will be the number of subjects that received the respective dose.

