9.3. Adverse Events

9.3.1. Solicited Events and Symptoms

Solicited adverse events collected 30 minutes post-vaccination (in-clinic assessment) and then daily for 7 days after each vaccination (through Day 8) will be graded on a scale of 0 (absent), 1 (mild), 2 (moderate) and 3 (severe). Local reactogenicity grading are provided in [Table 4](#) and [Table 5](#) and include:

- Pain – experienced without touching the injection site (spontaneous discomfort)
- Tenderness – hurts only when injection site is touched, or the arm is moved
- Erythema (Redness)
- Induration (Hardness/Swelling)
- Ecchymosis (Bruising)
- Pruritus (Itching)

The systemic reactogenicity grading is provided in [Table 6](#) and [Table 7](#) and includes:

- Feverishness (chills/shivering/sweating)
- Malaise (General Unwell Feeling)

- Fatigue (Tiredness)
- Myalgia (Body Aches/Muscular Pain)
- Headache
- Nausea
- Loss of Appetite
- Elevated Oral Temperature

Pre-second dose, safety events will include all safety assessments through Day 8 post-dose 1. If the second dose occurred on Day 8, Day 8 pre-second dose safety events will include memory aid assessments and in-clinical assessments that occurred prior to dose 2.

Safety data will be summarized for the Safety Analysis Population. Pre-second vaccination, Study Groups 1, 2, 3 will be analyzed jointly as one study group as all three groups received the same vaccine at Day 1.

[Table 23](#) will provide an overview of safety events by study arm and overall. Solicited AEs will be summarized using the maximum severity over all days after each vaccination overall by vaccination and symptom (subjects with mild or higher severity grading, [Table 24](#)) and by severity (none, mild, moderate, severe) and symptom ([Table 25](#)). In both cases, the resulting number, percentage (observed rate) of subjects and associated exact (Clopper-Pearson) 95% CIs by symptom, any systemic symptom, any local symptom, and any symptom (systematic or local symptom) will be provided. In addition, solicited AEs will be tabulated by severity for each day after each study vaccination (Days 1 through Day 8) following each vaccination ([Table 26](#) and [Figure 4](#)). Subject-level solicited events will be provided as shown in [Listing 10](#) and [Listing 11](#).

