Myalgia	x	x.x	x.x, x.x	x	x.x	x.x, x.x	x	x.x	x.x, x.x	x	x.x	x.x, x.x	x	x.x	x.x, x.x	x	x.x	x.x, x.x	x	x.x	x.x, x.x
Headache	x	x.x	x.x, x.x	x	x.x	x.x, x.x	x	x.x	x.x, x.x	x	x.x	x.x, x.x	x	x.x	x.x, x.x	x	x.x	x.x, x.x	x	x.x	x.x, x.x
Nausea	x	x.x	x.x, x.x	x	x.x	x.x, x.x	x	x.x	x.x, x.x	x	x.x	x.x, x.x	x	x.x	x.x, x.x	x	x.x	x.x, x.x	x	x.x	x.x, x.x
Loss of Appetite	x	x.x	x.x, x.x	x	x.x	x.x, x.x	x	x.x	x.x, x.x	x	x.x	x.x, x.x	x	x.x	x.x, x.x	x	x.x	x.x, x.x	x	x.x	x.x, x.x
Any Local Symptom	x	x.x	x.x, x.x	x	x.x	x.x, x.x	x	x.x	x.x, x.x	x	x.x	x.x, x.x	x	x.x	x.x, x.x	x	x.x	x.x, x.x	x	x.x	x.x, x.x
Pain	x	x.x	x.x, x.x	x	x.x	x.x, x.x	x	x.x	x.x, x.x	x	x.x	x.x, x.x	x	x.x	x.x, x.x	x	x.x	x.x, x.x	x	x.x	x.x, x.x

Table 24: Number and Percentage of Subjects Experiencing Solicited Events with 95% Confidence Intervals by Symptom, Dose, and Treatment Group (Continued)

Symptom	Post Dose 1 Study Arm 1,2,3 ChAd3 (N=X)*			Post Dose 2 Study Arm 1 ChAd3+Placebo (N=X)			Post Dose 2 Study Arm 2 ChAd3+ChAd3 (N=X)			Post Dose 2 Study Arm 3 ChAd3+MVA-BN (N=X)			Post Either Dose Study Arm 1 ChAd3+Placebo (N=X)			Post Either Dose Study Arm 2 ChAd3+ChAd3 (N=X)			Post Either Dose Study Arm 3 ChAd3+MVA-BN (N=X)		
	n	%	95% CI†	n	%	95% CI†	n	%	95% CI†	n	%	95% CI†	n	%	95% CI†	n	%	95% CI†	n	%	95% CI†
Tenderness	x	x.x	x.x, x.x	x	x.x	x.x, x.x	x	x.x	x.x, x.x	x	x.x	x.x, x.x	x	x.x	x.x, x.x	x	x.x	x.x, x.x	x	x.x	x.x, x.x
Pruritis	x	x.x	x.x, x.x	x	x.x	x.x, x.x	x	x.x	x.x, x.x	x	x.x	x.x, x.x	x	x.x	x.x, x.x	x	x.x	x.x, x.x	x	x.x	x.x, x.x
Ecchymosis (Functional Grade)	x	x.x	x.x, x.x	x	x.x	x.x, x.x	x	x.x	x.x, x.x	x	x.x	x.x, x.x	x	x.x	x.x, x.x	x	x.x	x.x, x.x	x	x.x	x.x, x.x
Ecchymosis (Measurement Grade)	x	x.x	x.x, x.x	x	x.x	x.x, x.x	x	x.x	x.x, x.x	x	x.x	x.x, x.x	x	x.x	x.x, x.x	x	x.x	x.x, x.x	x	x.x	x.x, x.x
Erythema (Functional Grade)	x	x.x	x.x, x.x	x	x.x	x.x, x.x	x	x.x	x.x, x.x	x	x.x	x.x, x.x	x	x.x	x.x, x.x	x	x.x	x.x, x.x	x	x.x	x.x, x.x
Erythema (Measurement Grade)	x	x.x	x.x, x.x	x	x.x	x.x, x.x	x	x.x	x.x, x.x	x	x.x	x.x, x.x	x	x.x	x.x, x.x	x	x.x	x.x, x.x	x	x.x	x.x, x.x
Induration (Functional Grade)	x	x.x	x.x, x.x	x	x.x	x.x, x.x	x	x.x	x.x, x.x	x	x.x	x.x, x.x	x	x.x	x.x, x.x	x	x.x	x.x, x.x	x	x.x	x.x, x.x
Induration (Measurement Grade)	x	x.x	x.x, x.x	x	x.x	x.x, x.x	x	x.x	x.x, x.x	x	x.x	x.x, x.x	x	x.x	x.x, x.x	x	x.x	x.x, x.x	x	x.x	x.x, x.x

N = Number of subjects in the Safety Population who received the specified dose.

*: Subjects in treatment groups that received the same study product were analyzed jointly.

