		n	%	95% CI	N	%	95% CI	n	%	95% CI	n	%	95% CI	n	%	95% CI	n	%	95% CI	n	%	95% CI
Induration (Functional grade)	None	x	x.x	x.x, x.x	x	x.x	x.x, x.x	x	x.x	x.x, x.x	x	x.x	x.x, x.x	x	x.x	x.x, x.x	x	x.x	x.x, x.x	x	x.x	x.x, x.x
	Mild	x	x.x	x.x, x.x	x	x.x	x.x, x.x	x	x.x	x.x, x.x	x	x.x	x.x, x.x	x	x.x	x.x, x.x	x	x.x	x.x, x.x	x	x.x	x.x, x.x
	Moderate	x	x.x	x.x, x.x	x	x.x	x.x, x.x	x	x.x	x.x, x.x	x	x.x	x.x, x.x	x	x.x	x.x, x.x	x	x.x	x.x, x.x	x	x.x	x.x, x.x
	Severe	x	x.x	x.x, x.x	x	x.x	x.x, x.x	x	x.x	x.x, x.x	x	x.x	x.x, x.x	x	x.x	x.x, x.x	x	x.x	x.x, x.x	x	x.x	x.x, x.x
Induration (Measurement grade)	None	x	x.x	x.x, x.x	x	x.x	x.x, x.x	x	x.x	x.x, x.x	x	x.x	x.x, x.x	x	x.x	x.x, x.x	x	x.x	x.x, x.x	x	x.x	x.x, x.x
	Mild	x	x.x	x.x, x.x	x	x.x	x.x, x.x	x	x.x	x.x, x.x	x	x.x	x.x, x.x	x	x.x	x.x, x.x	x	x.x	x.x, x.x	x	x.x	x.x, x.x
	Moderate	x	x.x	x.x, x.x	x	x.x	x.x, x.x	x	x.x	x.x, x.x	x	x.x	x.x, x.x	x	x.x	x.x, x.x	x	x.x	x.x, x.x	x	x.x	x.x, x.x
	Severe	x	x.x	x.x, x.x	x	x.x	x.x, x.x	x	x.x	x.x, x.x	x	x.x	x.x, x.x	x	x.x	x.x, x.x	x	x.x	x.x, x.x	x	x.x	x.x, x.x

N = Number of subjects in the Safety Analysis Population who received the specified dose.

Severity is the maximum severity reported over all solicited symptoms post dosing for each subject.

*: Subjects in treatment groups that received the same study product were analyzed jointly.

†: Based on Clopper-Pearson.

Table 26: Number and Percentage of Subjects Experiencing Solicited Events by Symptom, Severity, and Day (Study Arm 1, 2, and 3 (ChAD3) - Post Dose 1)

Symptom	Severity	Pre-Dose		Post-Dose		Day 1		Day 2		Day 3		Day 4		Day 5		Day 6		Day 7		Day 8	
		n	%	n	%	n	%	n	%	n	%	n	%	n	%	n	%	n	%	n	%
Any Symptom	None	x	x.x	x	x.x	x	x.x	x	x.x	x	x.x	x	x.x	x	x.x	x	x.x	x	x.x	x	x.x
	Mild	x	x.x	x	x.x	x	x.x	x	x.x	x	x.x	x	x.x	x	x.x	x	x.x	x	x.x	x	x.x
	Moderate	x	x.x	x	x.x	x	x.x	x	x.x	x	x.x	x	x.x	x	x.x	x	x.x	x	x.x	x	x.x
	Severe	x	x.x	x	x.x	x	x.x	x	x.x	x	x.x	x	x.x	x	x.x	x	x.x	x	x.x	x	x.x
	Not Reported	x	x.x	x	x.x	x	x.x	x	x.x	x	x.x	x	x.x	x	x.x	x	x.x	x	x.x	x	x.x
Systemic Symptoms																					
Any Systemic Symptom	None	x	x.x	x	x.x	x	x.x	x	x.x	x	x.x	x	x.x	x	x.x	x	x.x	x	x.x	x	x.x
	Mild	x	x.x	x	x.x	x	x.x	x	x.x	x	x.x	x	x.x	x	x.x	x	x.x	x	x.x	x	x.x
	Moderate	x	x.x	x	x.x	x	x.x	x	x.x	x	x.x	x	x.x	x	x.x	x	x.x	x	x.x	x	x.x
	Severe	x	x.x	x	x.x	x	x.x	x	x.x	x	x.x	x	x.x	x	x.x	x	x.x	x	x.x	x	x.x
	Not Reported	x	x.x	x	x.x	x	x.x	x	x.x	x	x.x	x	x.x	x	x.x	x	x.x	x	x.x	x	x.x
Elevated Oral Temperature	None	x	x.x	x	x.x	x	x.x	x	x.x	x	x.x	x	x.x	x	x.x	x	x.x	x	x.x	x	x.x

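### By-dose solicited-event rates are divided by everyone dosed, and Table 25 has no 'Not Reported' row, so a subject with no memory-aid data counts in effect as event-free

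*SAP*

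**What the plan says.** The first primary outcome in SAP 3.2.1 is "Frequency and severity of solicited local and systemic reactogenicity from the time of study vaccine administration through 7 days post-vaccination". SAP section 9 takes the safety population as the denominator for solicited and unsolicited events, except where results are shown by dose, "in which case the denominator will be the number of subjects that received the respective dose". The table shells repeat this. The Table 24 footnote reads "N = Number of subjects in the Safety Population who received the specified dose", and the Table 25 footnote reads "N = Number of subjects in the Safety Analysis Population who received the specified dose".

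SAP 9.3.1 summarises maximum severity "by severity (none, mild, moderate, severe) and symptom", and Protocol 11.4.2 names the same four grades. Table 25 follows suit: each symptom has rows for None, Mild, Moderate and Severe and nothing else. Its footnote says "Severity is the maximum severity reported over all solicited symptoms post dosing for each subject", with no rule for a subject who reported nothing.

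Table 26 (by day) does have a 'Not Reported' row for Any Symptom, the systemic symptoms and Any Local Symptom. It has none for pain, tenderness, pruritus, ecchymosis, erythema or induration. The laboratory and vital-sign shells (Tables 35 and 38) each carry a Missing column.

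**The concern.** Solicited events come from two sources: a clinic check 30 minutes after each injection, and the memory aid kept for 7 days. A subject who returns no memory-aid data for a dose has been observed for about half an hour of that week. Under the stated rule the subject still counts in full in the denominator.

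The trial tests no formal hypothesis and was sized to give preliminary estimates (Protocol 11.1, SAP 5). The rates and their exact intervals are therefore the primary result. A rule that can only push them down understates reactogenicity, and Tables 24 and 25 would not report how many subjects lacked data. The post-dose-2 columns, where the arms differ, hold about 20 subjects each. Memory-aid review is also sparser there: Days 2 and 8 after dose 2 (Protocol 7.3.3), against Days 2, 3, 4, 6 and 8 after dose 1 (Protocol Appendix A).

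**Working it through.** The documents give no expected rate or precision for this endpoint, so there is no planned figure to reproduce.

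**Inputs**
- N: 20 per arm and 60 in total (Protocol Table 1). The arms are pooled before the second dose (SAP 6.1).
- Illustrative rate p: 38.1% fever within 7 days at 1×10^11 pu, which Protocol 2.3.1 equates with the 2×10^11 vp used here. It follows a single ChAd3 dose, so using it for the second ChAd3 dose in Arm 2 is an assumption.
- Intervals: exact Clopper-Pearson, 95% (SAP 9.3.1).
- m, the number of dosed subjects with no memory-aid data and no event at the clinic check: not in the documents. I take 1 or 2.

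**Step 1. Does the choice of row matter?** Take 20 dosed, 8 with an event, 10 observed event-free and 2 with no data.
- Missing placed under None: None = 12/20 = 60.0%.
- Missing placed in no row: None = 10/20 = 50.0%, and the rows sum to 18/20 = 90%.
- Event rate either way: 8/20 = 40.0% (19.1 to 63.9).
- Among the 18 with data: 8/18 = 44.4% (21.5 to 69.2).

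The event rate and its interval are the same under both readings.

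**Step 2. Expected shift.** If missingness is unrelated to having an event, the expected reported rate is p × (N − m)/N.

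| Column | m = 1 | m = 2 |
|---|---|---|
| Post-dose-1, pooled, N = 60 | 0.381 × 59/60 = 37.5% | 0.381 × 58/60 = 36.8% |
| Post-dose-2, Arm 2, N = 20 | 0.381 × 19/20 = 36.2% | 0.381 × 18/20 = 34.3% |

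The understatement is 0.6 or 1.3 points in the pooled column and 1.9 or 3.8 points in the single-arm column.

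**Step 3. Events not seen.** With zero events the upper limit is 1 − 0.025^(1/n).
- One arm: 16.8% for 0/20, against 17.6% for 0/19 and 18.5% for 0/18.
- Pooled: 6.0% for 0/60, against 6.2% for 0/58.

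**Step 4. Who is affected.** Tables 24 and 25 use the maximum over all days, so one recorded reaction is enough to count. Only a subject with no memory-aid data for the dose and no event at the clinic check is affected.

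**The case against.** The strongest defence is that dividing by everyone dosed is an ordinary safety convention and matches Protocol 11.4.2, which summarises safety in the Safety Analysis Population. Missing diaries should also be rare: the memory aid is reviewed at several visits, including early-termination and unscheduled visits within 7 days of a dose, and Protocol 11.4.5 expects little missing data. Table 26 shows non-reporting by day for many rows, and Listings 10 and 11 give the subject-level records. In the Post Either Dose columns, a subject missing one diary still counts if the other dose produced an event. All of this stands, and it limits the size of the problem. It does not change the direction of the error or make it visible in Tables 24 and 25.

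A reader might infer three stronger things that the documents do not support:
- **The SAP assigns missing subjects to None.** No passage says so. They could equally sit in no row, and Step 1 shows that the event rate is unaffected.
- **SAP 6.5 contradicts section 9.** It says "missing data will be maintained as missing for all analyses and no imputation will be performed for missing values", but that sentence gives way where something else is specified. Section 9 specifies a denominator and imputes nothing. For the same reason, 6.5 does not remove these subjects from the denominator.
- **The bias is worst for people who stop reporting after a reaction.** Maximum severity already counts them at the grade they reported.

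**Conclusion.** The point holds as a minor but real fault in the analysis of a primary endpoint. The stated denominator gives a rate and an exact upper limit that are too low whenever a dosed subject has no memory-aid data and no event at the clinic check.

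With one or two such subjects, the shift is about one point in the pooled post-dose-1 column and two to four points in a 20-subject column at a 38% rate. Both the number missing and the rate are assumptions. If every memory aid is returned, nothing changes. The 38.1% figure should not be carried to the placebo or MVA-BN-Filo post-dose-2 columns, because it describes a ChAd3 dose. The omission looks like an oversight rather than a choice, since other shells in the same SAP provide for missing data.

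**What to change.** 1. Add a 'Not Reported' row to Table 25 and to the individual local-symptom rows of Table 26.
2. In SAP section 9 and the footnotes of Tables 24 and 25, base percentages and exact intervals on dosed subjects who have at least one memory-aid entry for the symptom or an event recorded at the in-clinic check. Show the number dosed alongside. The all-dosed rate may be kept as a second display.

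The wording of the denominator matters. Requiring a memory-aid entry alone would drop a reaction seen only at the 30-minute check. Accepting any post-dose solicited data would readmit nearly every dosed subject through that same check and change nothing.

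The cost is SAP wording and table shells. There are two downsides: denominators will differ slightly between symptoms, and keeping subjects known only from a clinic-check event tilts the rate marginally upward. The revised rate still assumes that subjects without data resemble those with data. In the Step 1 example, if both missing subjects had reacted, the rate would be 10/20 = 50.0% rather than 44.4%. Showing the number not reported lets a reader judge that.

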9.1. Demographic and Other Baseline Characteristics

Summaries of sex, ethnicity, and race will be presented by treatment group and overall ([Table 15](#)). Ethnicity is categorized as Hispanic or Latino, or not Hispanic and not Latino. In accordance with NIH reporting policy, subjects may self-designate as belonging to more than one race or may refuse to identify a race, the latter reflected in the CRF as “No” to each racial option. Age and body mass index (BMI) will be summarized as a continuous variable as outlined in [Table 16](#). All current and pre-existing medical conditions will be presented by MedDRA SOC and study arm ([Table 17](#)). Individual subject listings will be presented for all demographics ([Listing 6](#)); pre-existing and concurrent medical conditions ([Listing 7](#)); vital signs and oral temperature ([Listing 13](#)) and concomitant medications ([Listing 15](#)).

9.2. Measurements of Treatment Compliance

All subjects are to receive two doses of vaccine administered in the clinic. The first vaccination is given on Day 1, and the second (booster) vaccination is to be given on Day 8. [Table 14](#) summarizes the number of subjects who complied with the treatment administration schedule by study arm. Individual data listings of treatment compliance will be included in [Listing 3](#) and [Listing 8](#).

9.3. Adverse Events

9.3.1. Solicited Events and Symptoms

Solicited adverse events collected 30 minutes post-vaccination (in-clinic assessment) and then daily for 7 days after each vaccination (through Day 8) will be graded on a scale of 0 (absent), 1 (mild), 2 (moderate) and 3 (severe). Local reactogenicity grading are provided in [Table 4](#) and [Table 5](#) and include:

- Pain – experienced without touching the injection site (spontaneous discomfort)
- Tenderness – hurts only when injection site is touched, or the arm is moved
- Erythema (Redness)
- Induration (Hardness/Swelling)
- Ecchymosis (Bruising)
- Pruritus (Itching)

The systemic reactogenicity grading is provided in [Table 6](#) and [Table 7](#) and includes:

- Feverishness (chills/shivering/sweating)
- Malaise (General Unwell Feeling)

- Fatigue (Tiredness)
- Myalgia (Body Aches/Muscular Pain)
- Headache
- Nausea
- Loss of Appetite
- Elevated Oral Temperature

Pre-second dose, safety events will include all safety assessments through Day 8 post-dose 1. If the second dose occurred on Day 8, Day 8 pre-second dose safety events will include memory aid assessments and in-clinical assessments that occurred prior to dose 2.

Safety data will be summarized for the Safety Analysis Population. Pre-second vaccination, Study Groups 1, 2, 3 will be analyzed jointly as one study group as all three groups received the same vaccine at Day 1.

[Table 23](#) will provide an overview of safety events by study arm and overall. Solicited AEs will be summarized using the maximum severity over all days after each vaccination overall by vaccination and symptom (subjects with mild or higher severity grading, [Table 24](#)) and by severity (none, mild, moderate, severe) and symptom ([Table 25](#)). In both cases, the resulting number, percentage (observed rate) of subjects and associated exact (Clopper-Pearson) 95% CIs by symptom, any systemic symptom, any local symptom, and any symptom (systematic or local symptom) will be provided. In addition, solicited AEs will be tabulated by severity for each day after each study vaccination (Days 1 through Day 8) following each vaccination ([Table 26](#) and [Figure 4](#)). Subject-level solicited events will be provided as shown in [Listing 10](#) and [Listing 11](#).

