Fever within 7 days post-vaccination was observed in 5% of the subjects in the control group, in none of the subjects who received the 1×10^{10} pu dose, in 14.2% of the subjects who received 2.5×10^{10} pu, in 19.2% of the subjects who received 5×10^{10} pu and in 38.1% of the subjects in the 1×10^{11} pu groups. The only Grade 3 fever occurred with 5×10^{10} pu in the study ChAd3-EBOZ Lau. The onset of fever was mostly on Day 0-1 (except for 6 cases on Day 3-6) and fever was mostly self-limiting within 1 day. There was a clear dose-dependent increase in fever (any grade).

Transient non-clinically significant lymphopenia, neutropenia and anemia were observed within the first 28 days post vaccination with all doses (except neutropenia with 1×10^{11} pu) across all trials (including lymphopenia and neutropenia in the placebo control group in the study ChAd3-EBOZ Lau [only trial with a placebo control group]). The majority of these events were Grade 1. There is no evidence suggesting that the magnitude of these non-clinically significant changes increases with increasing vaccine dose.

Seven cases of transient platelet count drops met as per protocol criteria for thrombocytopenia ($<150 \times 10^9/L$), 4 in subjects who received 2.5×10^{10} pu and 3 in subjects who received 5×10^{10} pu. No clinical signs or symptoms suggestive of increased tendency for bleeding were reported. No thrombocytopenia was reported with 1×10^{10} and 1×10^{11} pu. Transient non-clinically significant drops in platelet count within 7 and within 28 days post-vaccination not meeting criteria for thrombocytopenia seem to be induced by vaccination ('real' phenomenon) i.e. seen consistently across trials and seen less frequently with in the placebo group included in the study ChAd3-EBOZ Lau.

No significant related unsolicited AEs were reported with any of the doses in any of the trials. No Suspected Unexpected Serious Adverse Reactions were reported. The only SAE reported to date (peritoneal tuberculosis 14 days post vaccination) is considered unrelated to vaccination.

Safety in Phase II Studies:

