4.2. Discussion of Study Design, Including the Choice of Control Groups

This was a double-blind clinical trial. Subjects, investigators, study personnel performing any study-related assessments were blinded to treatment arm assignment (i.e., type of booster). The inclusion of the Placebo boost allows for the assessment of the boosting effect for Study Arms 2 and 3 relative to a single dose (Study Arm 1) accounting for any Dose 1-related effects that extended beyond Day 8.

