4.4.3. Method of Assigning Subjects to Treatment Groups (Randomization)

Once consented and upon entry of demographic data and confirmation of eligibility for this trial, the subjects were enrolled. Subjects were randomized 1:1:1 in double-blind fashion to 1 dose of ChAd3-EBO-Z vaccine at Day 1 followed by a booster of placebo, ChAd3-EBO-Z (homologous), or MVA-BN®-Filo (heterologous) at Day 8.

Enrollment of subjects was done online using the enrollment module of AdvantageEDCSM. The randomization code was prepared by statisticians at the SDCC and included in the enrollment module for this trial. AdvantageEDCSM was used to assign each subject to a treatment arm after the demographic and eligibility data had been entered into the system.

Subjects who signed the informed consent form and were randomized but did not receive study vaccine may have been replaced. Subjects who signed the informed consent form, and were randomized and vaccinated, and subsequently withdrew, or were withdrawn or terminated from this trial, or were lost to follow-up might have been replaced.

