5. SAMPLE SIZE CONSIDERATIONS

This Phase I study is not designed to test a formal null hypothesis. The sample size for this study was selected to obtain preliminary estimates of vaccine safety and immunogenicity. The clinical trial includes an exploratory systems biology component to identify changes in gene expression, and cytokines that are associated with adaptive humoral and/or cellular immune responses. These systems biology results are expected to generate hypotheses to be verified in future studies.

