9.1 Overall Study Design and Plan Description

Table 1: Study Design

Subjects	First Study Vaccination (Day 1)	Second Study Vaccination (Day 8)	Study Arm Label
20	ChAd3-EBO-Z	Placebo	Study Arm 1 (ChAd3+Placebo)
20	ChAd3-EBO-Z	ChAd3-EBO-Z	Study Arm 2 (ChAd3+ChAd3)
20	ChAd3-EBO-Z	MVA-BN®-FILO	Study Arm 3 (ChAd3+MVA-BN)
Total N=60 subjects			

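### The placebo boost is there to measure the boosting effect, but the safety tables never estimate the difference between arms after Dose 2, nor compare Arm 2's second ChAd3 dose with its first

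*SAP*

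**What the plan says.** - **Purpose of the placebo boost (SAP 4.2).** "The inclusion of the Placebo boost allows for the assessment of the boosting effect for Study Arms 2 and 3 relative to a single dose", with allowance for first-dose effects that last beyond Day 8.
- **Solicited reactions (SAP 9.3.1, Tables 24-25).** The planned output is "the resulting number, percentage (observed rate) of subjects and associated exact (Clopper-Pearson) 95% CIs by symptom", plus the same for any local, any systemic and any symptom, and by severity. The columns are Post Dose 1 (three arms pooled), Post Dose 2 for each arm, and Post Either Dose for each arm. No difference, ratio or test between columns is planned. Table 26 gives daily results, again with Dose 1 pooled.
- **Denominators.** The Table 24 footnote reads "N = Number of subjects in the Safety Population who received the specified dose"; SAP 9 says the same for results shown by dose.
- **Antibody (SAP 8.1, Tables 21-22).** All three arm pairs are compared at each visit after the second vaccination: titre ratio and log2 difference with 95% CI, and odds ratio for seroconversion with 95% CI.
- **Who receives Dose 2 (Protocol 5.4.3).** Among other reasons, Dose 2 is withheld for a Grade 3 event that is still ongoing. It is also withheld for one within 7 days that lasts more than 24 hours without falling to a lower grade and has no other cause.
- **Inferential stance (SAP 5).** "This Phase I study is not designed to test a formal null hypothesis"; the sample size is meant to give preliminary estimates of safety and immunogenicity.

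**The concern.** The randomised, concurrent comparison with placebo after Dose 2 shows how much reactogenicity each boost adds. The plan estimates the corresponding quantity for the secondary antibody endpoint but not for the primary safety endpoint. Given only two separate intervals, many readers will check whether they overlap. That is a conservative guide: intervals that overlap are compatible with a difference whose own interval is well away from zero.

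There is a second gap. A further ChAd3 dose one week after the first is what distinguishes Arm 2. The planned summary tables do not show how Arm 2 subjects reacted to that dose compared with their own first dose. The nearest visible comparison is the Arm 2 Dose 2 column against a Dose 1 column pooled over all arms, and the Dose 2 column omits anyone who was not boosted.

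At stake is whether the report can state, with uncertainty, the added reactogenicity of each boost and the change from first to second ChAd3 dose.

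**Working it through.** The plan gives no power or precision figure to reproduce. The check asks what the planned display and the missing contrast would each show.

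**Inputs**
- 20 per arm: SAP Table 1 ("Total N=60 subjects") and SAP 4.4.3 ("Subjects were randomized 1:1:1 in double-blind fashion").
- Fever, Protocol 2.3.1: "Fever within 7 days post-vaccination was observed in 5% of the subjects in the control group", against 38.1% at 1×10^11 pu. The same section equates that dose with this trial's 2×10^11 vp.
- Adult Phase 2 pain, Protocol 2.3.1: 47.6% after ChAd3-EBO-Z, 7.6% in controls.
- Adult Phase 2 Grade 3 systemic events, Protocol 2.3.1: 2.8% after ChAd3-EBO-Z.

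These are first-dose rates used as stand-ins for Arm 2 and Arm 1 after Dose 2. They are illustrations, not predictions.

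**Step 1: one worked result (fever, 8/20 against 1/20)**
- Clopper-Pearson: 8/20 gives 19.1% to 63.9%; 1/20 gives 0.1% to 24.9%. They overlap between 19.1% and 24.9%.
- Wilson limits: 21.9% to 61.3%, and 0.9% to 23.6%.
- Newcombe interval for d = p1 − p2 = 0.40 − 0.05 = 0.35:
  - lower = d − √[(p1 − l1)² + (u2 − p2)²] = 0.35 − √[(0.400 − 0.219)² + (0.236 − 0.050)²] = 0.090
  - upper = d + √[(u1 − p1)² + (p2 − l2)²] = 0.35 + √[(0.613 − 0.400)² + (0.050 − 0.009)²] = 0.567
- The exact intervals overlap, yet the difference is 35 points (9.0 to 56.7).

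**Step 2: how often this happens**

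Every pair of counts (0 to 20 in each arm) was weighted by its binomial probability.

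| Illustrative rates | Exact intervals overlap | Newcombe CI excludes zero | Both |
|---|---|---|---|
| Fever 38.1% vs 5% | 73.5% | 76.8% | 50.3% |
| Pain 47.6% vs 7.6% | 59.9% | 86.0% | 45.9% |

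**Step 3: rare events**

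1/20 against 0/20 gives +5 points (−11.6 to 23.6). The contrast is uninformative here, and its interval says so.

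**Step 4: the Post Either Dose columns do not fill the gap**

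Assume independent reactions to the two doses.
- Fever in Arm 2: 1 − (1 − 0.381)² = 61.7%.
- Fever in Arm 1: 1 − (1 − 0.381)(1 − 0.05) = 41.2%.
- The post-Dose-2 difference of 33.1 points shrinks to 20.5.

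Nor do these columns give Arm 2's Dose 1 rate. Either-dose minus Dose 2 counts subjects who reacted to Dose 1 only; those who reacted to Dose 2 only and those who reacted to both remain merged.

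**Step 5: size of any selection effect on Dose 1 versus Dose 2**

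The documents give no number unboosted, so assume w from 0 to 6 of 60 and ignore replacement. In the worst case all w had the symptom and everyone else repeats their Dose 1 response: s/60 becomes (s − w)/(60 − w).
- Fever, s = 23: 38.3% becomes 36.2% (w = 2, −2.1 points) or 31.5% (w = 6, −6.9 points).
- Pain, s = 29: 48.3% becomes 46.6% (w = 2, −1.8) or 42.6% (w = 6, −5.7).
- Grade 3 systemic: 60 × 0.028 = 1.7 expected. With s = 2, 3.3% becomes 1.7% (w = 1) or 0% (w = 2).
- With w = 0, or no within-subject correlation, the expected shift is zero.

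For scale, the exact interval for 10/20 runs from 27.2% to 72.8%.

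**The case against.** The strongest reply is that this is a Phase 1 trial with no formal hypothesis. The objective is safety by study group, the outcomes are frequency and severity, and descriptive tables meet that. The three post-Dose-2 arms are printed next to each other with counts, denominators and intervals, so anyone can compute a difference. Nothing in the SAP tells readers to judge by overlap. Listings 10 and 11 carry subject and dose number, so paired data exist. SAP 4.2 does not say that the boosting effect means reactogenicity.

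Much of this stands. The arms are displayed together, so what is missing is an estimate, not the comparison itself. But the same SAP, under the same no-hypothesis statement, estimates arm contrasts for antibody, and an interval for a difference is an estimate, not a test. Listings are not a summary.

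A reader might go further and infer that the Dose 1 and Dose 2 columns hold different subjects, that every Grade 3 reactor is removed, or that the tables make Dose 2 look milder. The documents do not support these readings:
- Everyone in a Dose 2 column is also in the pooled Dose 1 column; it is a possibly selected subset.
- The two Grade 3 rules in Protocol 5.4.3 cover ongoing or persistent events. One that settles within a day does not by itself bar Dose 2 under them, and Protocol 2.3.1 describes systemic events as generally self-limiting within 24 hours.
- A milder appearance needs both unboosted reactors and within-subject correlation, and the documents establish neither.

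Selection also gives no reason to doubt the randomised post-Dose-2 comparison: withholding follows the same product in every arm, with assessors blinded.

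**Conclusion.** The point holds as a reporting gap in the primary safety analysis, not as an error in a stated figure or a bias in the randomised comparison. The placebo boost's stated purpose has no matching between-arm estimate for reactogenicity. For common reactions that matters: at the illustrative fever rates, in about half of trials the separate intervals overlap although the interval for the difference excludes zero. For Grade 3 events the added contrast will say little at 20 per arm.

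The missing within-subject view of Arm 2 also holds. Any distortion from withheld second doses is possible but undemonstrated: zero if all are boosted, and at most about 7 points for fever or pain under the worst case with 6 of 60 unboosted. It could remove a Grade 3 signal of one or two subjects.

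The figures assume that first-dose rates from other studies carry over to the boost and that about 20 per arm receive it. The range of 0 to 6 unboosted is an assumption. The change is worth making because it is cheap; the descriptive plan is defensible without it but says less than the data allow.

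**What to change.** Add to SAP 9.3.1, among subjects who received Dose 2:

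1. Post-Dose-2 risk differences with 95% CIs (Newcombe or Miettinen-Nurminen; name one in advance) for Arm 2 minus Arm 1, Arm 3 minus Arm 1 and Arm 3 minus Arm 2. Report them for any local symptom, any systemic symptom, any symptom of moderate or worse grade, and fever: 3 × 4 = 12 rows. Label them descriptive, with no p-values and no multiplicity claim. The third pair covers homologous against heterologous boosting, which the rationale in SAP 2.2 names.
2. For Arm 2 subjects who received both doses, a paired Dose 1 by Dose 2 table for the same four outcomes, with the paired difference and its 95% CI. Footnote that dose order cannot be separated from dose effect, and that diaries were reviewed more often after Dose 1 (Days 2, 3, 4 and 6, then the Day 8 visit) than after Dose 2 (Days 2 and 8). State how many Arm 2 subjects did not receive Dose 2 and why.

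The cost is one or two extra tables from data already collected. Intervals will be wide for rare events and should be shown as they are.
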